**You can upload charts or diagrams if any**

- Table1PSF%OTVP%.pdf
- Table2PSF%OTVP 14 (1).pdf
- Figure 1 PSF%OTVPDay 1version2.pdf
- Study assessmentstable4PSF%OTVP.pdf

**Criteria for Early Discontinuation**

**Criteria for Early Discontinuation**

Removal from participation from the study can take place under several circumstances: 1) emergence of a medical condition unrelated to the study that would render continued participation unsafe; 2) psychiatric worsening, such as emergence of depression (HamD score >17), psychosis (HamD item 22 >3), or of other significant psychiatric symptoms such as suicidality (HamD item 15 > 3). **Each of these conditions, presenting separately or together, in any combination, which would lead the reviewing clinical to rate a CGI score > 6 for two consecutive weeks;**

3) substance abuse worsening as assessed by clinicians on the research team during weekly visits, as evidenced by a CGI score >6 for two consecutive weeks; 4) emergence of hyponatremia during the study as indicated by a sodium concentration < 133 mEq/L or early symptoms such as asthenia, fatigue, nausea, vomiting, and weakness; 5) missing one week of supervised clinic-based administration of IN oxytocin or placebo. Participation in the study is voluntary and patients can withdraw at any time. In each instance, they will be offered referrals for ongoing treatment.

The study will be stopped if 3 patients develop hyponatremia during the course of the study.

## Blood and other Biological Samples

**Please create or insert a table describing the proposed collection of blood or other biological specimens**

Blood draws for this study are as follows:

1: During screening, approximately 12 .5 ccs (one tablespoon) of blood is drawn for electrolytes, hepatic panel, blood counts analyses for both cocaine dependent patients and controls.

2: During phase 1, blood samples are taken as part of the stress challenge testing. Day 1 testing involves 64 ccs of blood (8 tubes) for measurement of ACTH. Day 2 involves 88 ccs of blood (11 tubes) for measurement of ACTH. This applies for control and cocaine-dependent participants. These samples are drawn through a saline catheter.

3: During Phase 2, at weeks 2, 4, and 6, medical monitoring involves a blood draw to review electrolytes, hepatic function, blood counts. This equals 24 ccs of blood (3 tubes). This applies only to cocaine-dependent patients.

4: At the end of phase 2, Day 1 of the stress challenge is repeated. This involves 64 ccs of blood (8 tubes) for analysis of ACTH. This applies only to cocaine dependent patients. These samples are drawn through a saline catheter.

5: For control participants, the total volume of blood drawn during their participation in screening and phase 1 would be 164.5 ccs of blood, approximately 17 tablespoons.

6: For cocaine-dependent patients, the total volume of blood drawn during screening, phase 1 and phase 2 would total 198.5 ccs of blood, approximately 20 tablespoons.

## Assessment Instruments

**Create a table or give a brief description of the instruments that will be used for assessment**

Mini Neuropsychiatric Interview (MINI)	45 minutes
Time Line Follow Back (TLFB)	5 minutes
Behavioral Activation Scale (BAS)	2 minutes
Clinician Global Impression-Observer (CGI-O)	1 minute

---

Hamilton Depression Scale-25 items (HAM-D)	5 minutes
Perceived Stress Scale (PSS)	2 minutes
Cocaine Craving Scale (CCS)	2 minutes
Lickert Scales for cocaine craving, agitation during Stress challenge (0 to 10, 10 = worse)	1 minute

**Please attach copies, unless standard instruments are used**

### Off label and investigational use of drugs/devices

**Choose from the following that will be applicable to your study**

Drug

**Select the number of drugs used in this study**

2

**Drug #1**

**Name of the drug**

desmopressin

**Manufacturer and other information**

Part of the relevant information is already described in the uploaded PSF

Desmopressin is a synthetic vasopressin analog, with greatest affinity to the V1b receptor. It will be used to test a form of stress adaptation that we think might be present in cocaine-dependent patients.

The main reported side effects of intranasal desmopressin is abdominal pain (2%), headache (2%), epistaxis (3%), nostril pain (2%), rhinitis (8%), and conjunctivitis (2%) (PDR, 2014). There is remote possibility of hyponatremia. How this will be monitored and approached is discussed in the risk section.

The manufacturer is Apothec or Sanofi Aventis Inc. It will be ordered by our research pharmacy and dispensed from there.

---

The use of desmopressin is being reviewed by the FDA under a single IND also involving the use of intranasal oxytocin: IND#: 122630.

**Approval Status**

IND is approved

**IND#**

122630

**Who holds the IND/IND sponsor?**

IND is held by PI/CU Investigator

[name]

**Drug #2**

**Name of the drug**

oxytocin

**Manufacturer and other information**

Part of the relevant information is already uploaded in the PSF

Intranasal oxytocin is being tested in cocaine-dependent patients to see if it would mitigate a form of stress that they may develop, which contribute to increasing their relapse risk.

In published reports on the use of intranasal oxytocin, noted side-effects were: light-headedness, anxiety, clouded thinking, and transient nasal cavity irritation. There is a remote possibility of hyponatremia. In the published reports on the investigational use of intranasal oxytocin, there has not been one instance of this complication. How this will be monitored and approached is discussed in the risk section

Intranasal oxytocin is not available by prescription, hence not approved by the FDA for clinical use. We will use Syntocinon prepared by Novartis, Switzerland. Victoria Pharmacy Zurich Switzerland will the packaging for international shipment. They will also prepare matching placebo solutions.

**Approval Status**

IND is approved

---

**IND#**

122630

**Who holds the IND/IND sponsor?**

IND is held by PI/CU Investigator  
[name]

**Research Related Delay to Treatment**

**Will research procedures result in a delay to treatment?**

Yes

**Maximum duration of delay to any treatment**

What is maximum duration of delay due to research procedures before patient begins a treatment of any kind?

The delay to treatment is the delay required for baseline workup; once a cocaine-dependent patient enters the trial, it begins with an in-hospital phase, guaranteeing abstinence, or participates in an outpatient version of phase 1 should it not be possible to be hospitalized for 5 to 7 days. The baseline workup can easily be completed when a patient attends their first screening appointment. Delays extending beyond this are usually due to scheduling conflicts, or further evaluations being needed to clarify medical or psychiatric issues. In more complicated cases, at the most, two to three weeks may be required to complete the work-up and determine eligibility.

**Maximum duration of delay to standard care or treatment of known efficacy**

What is maximum duration of delay before active treatment (medication or psychotherapy) that is part of routine care or of known efficacy is offered? (Include time period described in B. above.)

The delay for effective treatment for cocaine dependence is the time for baseline work-up as noted in 4B. The first part of the trial is an in-hospital stay, or an outpatient version, during which breaking the cycle of addiction to cocaine is attempted. Being unable to do so is the very situation that often brings people to treatment. They also participate in extensive testing, which highlights some of their precipitants to cocaine use. This material can be integrated into the supportive therapy in the trial. Compliance Enhancement is a behavioral therapy with demonstrated efficacy for substance dependence disorders (Carroll & O'Malley, 1996; Pettinati et al., 2005). Patients will be monitored at all times for clinical worsening, and can be removed from the trial at any point to be offered treatment as clinically indicated.

---

### **Treatment to be provided at the end of the study**

Describe treatment to be provided (if any, including duration) at the end of the study.

At the end of phase 2, the patient will have the opportunity to meet with their therapist for 3 more sessions to help with the transition of ending the study, and if they wish, continue treatment at another location. STARS or DOSA staff will continue to work with patients until alternative treatment is found. Patients participating in the NEXT STEP program at DOSA can continue in this program.

### **Clinical Treatment Alternatives**

#### **Clinical treatment alternatives**

This proposal offers procedures that themselves are part of recognized treatment approaches to cocaine dependence. The procedures described here are based in part on protocol 6013, which studies the effects of mifepristone in humans to treat cocaine dependence.

We have used in hospital treatment for detoxification as a well-established method of first intervention in cocaine dependence. It is readily appreciated by most patients that if they could stop on their own, in their own home, they would have done so. Compliance enhancement therapy (Carroll et al., 1994), coupled with voucher incentives (Higgins et al., 1994) provide behavioral treatments with demonstrated efficacy.

If patients contacting STARS cannot qualify, we will offer referrals to clinical treatment. For patients contacting DoSA, participation in the Next Steps program is an option, with or without participation in the study. Patients completing the study can continue at Next Steps.

### **Risks/Discomforts/Inconveniences**

#### **Risks that could be encountered during the study period**

Risks to subjects.

1. We expect few side effects and adverse events from the medication tested in this clinical trial, given the total dosing and frequency of administration.
  
2. More common side effects encountered with IN administration are nasal irritation, nasal congestion, nasal discharge, and potentially atrophic rhinitis. This may be particularly so for intranasal cocaine users with damaged nasal mucosa. This will be specifically monitored for during clinic visits.
  
3. Desmopressin (Vasopressin analog): Desmopressin is used to treat central diabetes insipidus. Daily dosing can be up to 0.8 mg po/day (or up 3200 IU). The most severe complication that can arise from use of desmopressin (PO or IN) on a daily basis for a prolonged period of time is excessive renal water reabsorption and hyponatremia. Signs and symptoms of emerging hyponatremia include: headache, nausea/vomiting, decreasing serum sodium, weight gain, fatigue, lethargy, depressed reflexes, muscle weakness, spasms, or cramps, change in mental status, disorientation, and coma. This rarely develops from administration of a single or a few consecutive daily doses. During their participation, control participants will receive 2 consecutive doses of IN desmopressin (total = 160 IU); cocaine-dependent patients receive 3 doses of IN desmopressin (total = 240 IU), two during phase 1 and one at the end of phase 2. In the one publication where a somewhat comparable approach was used (Araya et al., 2006), no side effects from desmopressin IV was noted.
  
4. Oxytocin: Oxytocin is used during labor and delivery to promote uterine contraction. In this instance, doses vary, but far exceed the daily dose of 24 IU/day used in this study. Administered intravenously as Pitocin, it can also lead to hyponatremia, arrhythmia, convulsions, chest pain, shortness of breath, confusion, swelling, headache, nausea/vomiting, cardiac arrhythmia. During their participation, control participants will receive 2 consecutive doses of IN oxytocin (40 IU in total) during phase 1. Cocaine-dependent patients receive 47 doses of IN oxytocin (940 IU) over a period of 7 weeks. No serious adverse events arose in a study during which 40 IU were administered daily for one week, then 80IU/day for another 7 weeks (Modabbernia et al., 2013). Feeling too relaxed, light-headedness, anxiety, clouded thinking, and nasal cavity irritation are the most common side effects reported in protocols approximating the one presented here (Rodrigues et al., 2009; Ditzen et al., 2009).
  
5. Another potential risk, especially for intranasal cocaine users, is whether the use of the intranasal approach would serve as a trigger for cocaine use. As this pharmacological approach has not been investigated before, this will be specifically queried for during clinic-based administration.
  
6. No data exists examining the risk of cocaine use is enhanced by concomitant intake of oxytocin. We

---

do not anticipate that it would increase the risk of cocaine use. As change in cocaine use is a main outcome of the study, evidence of increased cocaine use will be monitored closely.

7. The stress challenge may cause patients to experience cravings for cocaine. After each procedure, a gradual muscle relaxation procedure will be used to reduce these.
  
8. Vouchers could be exchanged for drugs, or their monetary value could serve as a trigger to procure cocaine. Expending vouchers is a major topic of the counseling during the study to promote a drug-free lifestyle.
  
9. The structured interviews, self-reports, and questionnaires should not pose a physical risk. Their disadvantage is the time to complete them. Our past experience using these measures indicates that patients find them acceptable.
  
10. The risk of the blood tests is the discomfort associated with venipuncture, and a possibility of slight bruising. For the stress challenge, a saline lock will be placed to avoid repeated venipuncture.
  
11. Patients applying for, or admitted to treatment divulge information, such as drug use, which is sensitive and may have adverse social consequences if released. This would include information released to insurance companies, family members, or made public in any way. All clinical and research records will be treated with the confidentiality accorded any medical record in a substance abuse treatment setting. We will also apply for a certificate of confidentiality for this trial.

### **Describe procedures for minimizing risks**

Procedures to minimize risk.

The exclusion criteria are designed to minimize the medical and psychiatric risks to participants. Potential participants will not enter the study should they present with a psychiatric disorder,

---

suicidality risk; except major depression provided it is in remission as attested by a HamD score <8. The baseline medical evaluation includes a history, review of systems, a physical examination, blood chemistry profile including electrolyte (Na, K, Cl, Ca, CO3), liver function test, blood count, urinalysis, urine pregnancy test, and electrocardiogram. It is designed to detect unstable medical conditions that would be prejudicial to participation in the study. Since the most serious potential adverse event is water toxicity and hyponatremia (Na < 133 mEq/L), the screening will focus closely on any signs and symptoms of hyponatremia, which include: nausea, vomiting, headache, confusion, loss of energy, fatigue, restlessness and irritability, muscle weakness, spasms, or cramps, seizures, unconsciousness, and coma. The medical, psychiatric, and laboratory screening is such that hyponatremia, or risks of hyponatremia (medications, renal failure), will be brought forth. Should hyponatremia emerge (Na < 133 mEq/L), whether symptoms are present or not, during the clinical trial, clinic-based and at-home administration of randomized medication will be interrupted, and the patient monitored by daily blood draws to monitor progress, together with encouragement to consume salt containing fluids. Should symptoms and signs appear or worsen, the patient will be referred to an emergency room for electrolyte management. Feeling too relaxed, light-headedness, anxiety, clouded thinking, and nasal cavity irritation are the most common side effects reported in protocols approximating the one presented here (Rodrigues et al., 2009; Ditzen et al., 2009). Symptoms of nasal irritation can occur from nasal administration. We will monitor this during clinic-based administration. This irritation may be more likely in intranasal cocaine users because of pre-existing irritation and damage to the nasal mucosa. No specific intervention is contemplated for this, except that nasal mucosa with preserved olfaction regenerates rapidly. Reduction in consumption or abstinence from cocaine may reduce this problem. Intranasal administration could be a trigger for further cocaine use. The Cocaine Craving Scale will be administered after clinic-based administration. Should cravings be reported, relaxation exercises (as performed in IRB protocol 6013) conducted with the patient by a member of the research staff can assuage the cravings. Whether the intranasal route is itself a trigger in cocaine-dependent patients is an important measure of the feasibility of this approach. The screening, consent, and study visit procedures are designed to safeguard the patient's welfare during their participation. The principal investigator and research staff extensively review and explain procedures, monitor the patient's status to review progress, side-effects, and adverse events. The purpose and procedures of the stress sensitivity testing will be thoroughly explained. Studying stress parameters can help determine if targeting these represents a valid approach to the treatment of cocaine dependence. Post-stress challenge relaxation exercise (already used in Protocol 6013) can help reduce the induced stress. This is especially important for patients choosing the outpatient abstinence induction procedure. We ask patients to give us names of person whom they trust who we can contact during the study should not be able to contact them through their regular number. We emphasize to them that although not mandatory, it is an important safety issue, in case we need to contact them urgently, or reschedule missed appointments. Removal from participation from the study can take place under several circumstances: 1) emergence of a medical condition unrelated to the study that would render continued participation unsafe; 2) psychiatric worsening, such as emergence of depression (HamD score >17), psychosis (HamD item 22 >3), or of other significant psychiatric symptoms such as suicidality (HamD item 15 > 3), culminating in a CGI score > 6 for two consecutive weeks; 3) substance abuse worsening as assessed by clinicians on the research team during weekly visits, as evidenced by a CGI score >6 for two consecutive weeks; 4) emergence of hyponatremia during the study as indicated by a

sodium concentration < 130 mEq/L or early symptoms such as asthenia, fatigue, nausea, vomiting, and weakness; 5) missing one week of supervised clinic-based administration of IN oxytoxin or placebo. Participation in the study is voluntary and patients can withdraw at any time. In each instance, they will be offered referrals for ongoing treatment. The study will be stopped if 3 patients develop hyponatremia during the course of the study.

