This procedure is based on our previous experience acquired during protocol NYSPI IRB 6013 (mifepristone study for cocaine dependence) with patients who cannot participate in the inpatient procedure. Over a period of 7 days, not counting Saturdays and Sundays, a participant will have to produce at least three consecutive cocaine negative urine toxicologies at daily visits. Once abstinence is established the phase 1 procedures begin (Table 1), with verification of negative toxicology before each testing day. Randomized medication will begin after completion of all the physiological tests.

---

If a urine toxicology test emerges positive for cocaine once Phase-1 procedures have begun, the testing will stop. The patient can then attempt another period of seven days to reach abstinence, complete the baseline testing, and begin randomized medication. If abstinence cannot be reached during this two-week window, the patient will be offered to carry out phase 1 as an inpatient. If the patient cannot participate as an inpatient, referrals to other treatment options will be offered.

Phase 2, outpatient phase, week 2 to 7, cocaine-dependent patients only

During this phase in which only cocaine-dependent patients participate, they will continue randomized medication while participating in a structured program to support and promote continuing abstinence and completion of the study.

For patients continuing at the STARS clinic and DOSA at Waters Place ([name]), the structure of the program during this phase will be as follows:

- 1: Patients continue to receive intranasal Oxytocin (24IU/day) vs. intranasal placebo. During their visits to either clinic, they will administer the randomized medication under supervision from a bottle kept at the clinic. Each witnessed administration will be recorded. Since they "self-administer" the medication, it can be witnessed by any member of the research team.

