- 2: On the days when patients do not attend the clinic, they will be asked to administer the randomized medication from an "at-home" bottle. They will be asked to bring the bottle at each visit to the clinic. In a single-blind fashion, it will be weighed as a measure of compliance. The metered bottle delivers 4 IU/0.1cc or per puff. Each daily dosing requires 6 puffs, or 0.6cc. The weight of each puff or 0.1 cc is approximately 0.1g. Hence, for each at-home insufflation, the bottle weight is expected to change by 600 mg. The expected change in weight will be plotted against the recorded change in weight, and this will be used to estimate at-home compliance.
- 3: At each visit, vital signs are recorded, and an inquiry is made about adverse events. The Time-Line-Follow-Back is completed to review drug use by calendar date. This allows a day-to-day review of reported drug use for each day of participation.
- 4: At week 2, 4, and 6, a thorough medical review will be carried out to ensure patient safety. This will include a review of systems, with a focus on lethargy, fatigue, nausea, and weakness, which are the usual symptoms of hyponatremia. Although the risk is remote, hyponatremia would be the major metabolic complication that could arise from intranasal oxytocin. Of note is the fact that it has been reported when oxytocin is used in the induction of labor with continuous intravenous infusion (Pitocin, PDR, 2014), a condition vastly different from those of this study. A blood draw will be done to monitor electrolytes and

---

blood counts. For women, a urine pregnancy test will also be done. Detection of pregnancy ends participation in the study.

5: Self-reports that will be completed weekly at one of the visits: Perceived Stress Scale, Cocaine Craving Scale.

6: The vital sign form, the review of system form (including blood results) will be dated and will refer to a calendar date of the clinical trial week it was performed to ensure proper recording.

7: At one of the visit, patients will meet with a research psychiatrist to review participation, whether progress or regress is being made, and to complete clinical ratings that will include a Substance Use Inventory, the Clinical Global Impression scale, a medical review, and completion of all clinical notes. All these forms are dated. These are then recorded in the clinical trial week form that corresponds to the calendar dates for that week.

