14. PROJECT DIRECTOR/PRINCIPAL INVESTIGATOR CONTACT INFORMATION
Prefix: Dr. * First Name: [name] Middle Name: N
* Last Name: [name] Suffix:
Position/Title: Research Scientist level VI
* Organization Name: Research Foundation for Mental Hygiene, Inc.
Department: 110 NYPI Substance Abuse Division:
* Street1: NYPI
Street2: [name]
* City: New York County / Parish: New York
* State: NY: New York Province:
* Country: USA: UNITED STATES * ZIP / Postal Code: 10032
* [contact] [contact]
* Email: [contact]

2) Cocaine Craving Scale (CCS, Weiss et al., 1997); 3) Subjective ratings of cocaine craving, depression, anxiety, stress during stress testing (Likert scale 0 to 10, 10 = worse) Physiological tests: 1) Nine drug urine toxicology (Iscreen™ 9 drugs); 2) Stress Sensitivity Testing: serum ACTH, HR, BP for Day 1 and Day 2 (see table 2.)

Phase 2 Measures: The goal of phase 2 is to test if IN OT can reduce relapse risk. Measures collected may inform *Primary Aim 2, Secondary Hypotheses, and Exploratory Aims a, b* (section 3.4). **Compliance monitoring:** a) Witnessed, and recorded insufflations of IN OT vs. Pbo, 3x/wk from a bottle kept refrigerated at STARS; b) Patients will be instructed on storing and using the nasal spray bottle before At-home insufflation begins. They will be told to bring this bottle with them at every visit. [*Monitoring: unbeknownst* to the patient, the at-home bottle will be weighed before being given, and will be weighed at every visit. The metered bottle delivers 5 IU/0.1cc or per puff. Each daily dose requires 4 puffs or 0.4 cc. The weight of each puff or 0.1cc is approximately 0.1g, hence for each at-home insufflation, the bottle weight is expected to change by 400 mg. The expected weight change will be compared to the actual recorded weight.] **Medical monitoring:** a) electrolyte: (Na, K, Cl), spot cortisol, urine pregnancy test for women at week 2, 4, 6; b) weekly medical review for signs and symptoms of hyponatremia and side effects. **Clinician Interviews:** 1) TLFB 3x/wk; 2) CGI-O 1x/wk; 3) Adverse event form 3x/wk; 4) HamD 1x/wk. **Self reports:** 1) PSS 1x/week, 2) CCS 3x/week. 3) subjective ratings of depression, anxiety, stress and cocaine craving (Likert scale 0 to 10) and BAS (table 2). **Physiological tests:** *Stress sensitivity testing:* repeat of Day 1 IN DDAVP 80 IU challenge, ACTH, HR, BP; 2) *Nine drug urine toxicology, 3x/wk.*

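### No planned contrast isolates whether the intranasal route triggers craving: in Phase 2 the craving scale is timed only after the supervised spray, both arms spray, and no analysis of it is planned

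*Protocol*

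**What the plan says.** The protocol's section on minimizing risks warns that "Intranasal administration could be a trigger for further cocaine use" and adds: "Whether the intranasal route is itself a trigger in cocaine-dependent patients is an important measure of the feasibility of this approach". Between those two statements it places the measurement: "The Cocaine Craving Scale will be administered after clinic-based administration". If craving is reported, staff can offer relaxation exercises.

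The list of risks (item 5) raises the same question, "whether the use of the intranasal approach would serve as a trigger for cocaine use", with intranasal cocaine users as the main worry, and promises that "this will be specifically queried for during clinic-based administration". It gives no form, comparator or analysis for that query.

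Both Phase 2 arms spray: "Patients continue to receive intranasal Oxytocin (24IU/day) vs. intranasal placebo" (Study Procedures, Phase 2, item 1).

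The frequency of the scale is stated in two ways. Study Procedures, Phase 2, item 5 has "Self-reports that will be completed weekly at one of the visits: Perceived Stress Scale, Cocaine Craving Scale". The SAP's Phase 2 Measures have "1) PSS 1x/week, 2) CCS 3x/week".

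Feasibility heads the secondary hypotheses in both documents, but the two hypotheses that follow concern cocaine using days. SAP section 3.4.1 lists craving as an outcome for the Phase 1 challenge only. The Phase 2 outcomes there are consecutive abstinent days and cocaine using days.

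**The concern.** The protocol sets itself a question about the route of administration, distinct from the drug. Answering it needs a comparison in which the spray is present on one side and absent on the other, either between patients or within a patient over a short interval. The Phase 2 plan provides neither. A score of 5 after the spray could be that patient's usual craving or a rise caused by spraying.

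If this stays as it is, the trial will collect many craving scores after the spray and still be unable to say whether a nasal spray suits this population. The answer matters most for patients who took cocaine intranasally. The primary outcome is not at stake.

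**Working it through.** The documents give no sample size, precision or threshold for this question, so there is no stated figure to reproduce. The check has two parts.

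**1. What each available measurement can identify**

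Write a Phase 2 score after the spray as resting craving (R), plus any route effect (S), plus any oxytocin effect (D).

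- Placebo arm, after the spray: R + S. Oxytocin arm, after the spray: R + S + D.
- Oxytocin minus placebo: D. The route effect S cancels, whatever the sample size.
- Placebo arm alone: R + S is one number with two unknowns.
- Placebo arm, after minus before the spray, if a prior rating were taken: S plus any change due to time and the visit itself.

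Other sources in the plan:

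| Source | What it offers | Why it does not isolate the route |
|---|---|---|
| Phase 1 stress challenges (Study Procedures, item 4) | Likert craving before and after insufflation, including ratings between oxytocin and the desmopressin given 40 minutes later | Every spray is active desmopressin or oxytocin; there is no placebo-spray or no-spray session |
| Baseline Cocaine Craving Scale (Phase 1, item 2) | A value before randomised medication starts | Not paired with a dose |
| Direct query (risks, item 5) | The patient's own attribution | No form, comparator or analysis stated |
| Route of cocaine use (stratum and covariate, SAP 3.4.1 and 3.4.2) | Intranasal users against smokers | On scores after the spray only, it mixes differences in resting craving with differences in triggering |

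None of these is planned as a test of the route.

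**2. What a rating before the spray would give**

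Inputs from the documents: 3 visits a week for 6 weeks = 18 supervised visits at most; 25 patients planned per arm; 26 randomised as reported at the end of the SAP (15 oxytocin, 11 placebo); craving items scored 0 to 9 (SAP, Study Assessments).

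Assumed, because the documents give no value: standard deviation of the within-visit change 2; between-patient standard deviation of the mean change 0.5 to 1.

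Standard error = √((between-patient SD² + 2²/visits) / patients). The 95% half-width is t × standard error.

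- 11 placebo patients, 18 visits, t(10) = 2.228: √((0.25 + 0.222)/11) = 0.207, giving ±0.46; √((1 + 0.222)/11) = 0.333, giving ±0.74.
- 25 placebo patients as planned, 18 visits, t(24) = 2.064: √(0.472/25) = 0.137, giving ±0.28; √(1.222/25) = 0.221, giving ±0.46.
- 26 patients pooled over arms, 18 visits, t(25) = 2.060: √(0.472/26) = 0.135, giving ±0.28; √(1.222/26) = 0.217, giving ±0.45.
- 11 placebo patients, 6 visits (weekly scale): √((0.25 + 0.667)/11) = 0.289, giving ±0.64; √((1 + 0.667)/11) = 0.389, giving ±0.87.

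For the split by route of cocaine use, the documents do not give the proportions. With 50 patients and 80% power at two-sided 5%, the detectable difference is 1.01 SD if 20% are intranasal users, 0.88 SD if 30%, and 0.81 SD if 50%. That supports a descriptive split, not a test.

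**The case against.** A reader might infer that craving is never rated before a spray anywhere in the study, or that no estimate of any kind is possible. The documents do not support either reading. In the Phase 1 challenges, patients rate craving before insufflation and again afterwards, and a baseline craving scale is taken before randomised medication. These contrasts exist. They are confounded with active peptide, and none is planned as a test of the route.

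Four further points deserve weight.

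- Craving is rated after the dose in a risk-minimisation section, where finding patients who need a relaxation exercise is a sufficient purpose. That stands for the safety response. The same section, however, also makes the route question a measure of feasibility, which this timing cannot serve.
- Asking patients directly whether the spray provoked craving needs no prior score. That is fair, but the query is unspecified and nothing is planned for its answers.
- The stated worry is cocaine use, which is tracked by self-report and urine toxicology three times a week. But both arms spray, so the randomised comparison of use cannot isolate the route either.
- A before-and-after change is imperfect. It has no no-spray comparator, and a rating taken just before an expected spray may already contain anticipatory craving. Pooling the arms could also let an oxytocin reduction hide a rise due to the route, since the first-phase hypotheses expect oxytocin to lower subjective ratings, which in the SAP include craving. This stands, and is why the placebo arm should carry the main estimate.

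Only the risk-minimisation section times the scale relative to the dose; the weekly and three-times-weekly statements do not. A prior rating is therefore unspecified rather than ruled out. The protocol's Table 3 cannot settle the frequency, because its craving row is merged with another instrument.

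**Conclusion.** The point holds for the supervised Phase 2 spray. The only scale tied to the dose follows it, both arms spray, and no craving, route or feasibility analysis is specified, so no planned contrast isolates whether the intranasal route triggers craving. The gap concerns a feasibility question that the protocol itself calls important; it does not touch the primary analysis.

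The gap can be narrowed cheaply. On the assumed standard deviations and 18 visits, the mean change would be known to about ±0.46 to ±0.74 points with the 11 placebo patients reported, or ±0.28 to ±0.46 with the planned 25. The pooled figure for 26 patients, ±0.28 to ±0.45, is tighter but mixes drug with route. Missed visits, dropout (the SAP anticipates 30%) or a weekly scale would widen all of these. The standard deviations have no source in the documents, so the figures are illustrative.

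**What to change.** - At supervised Phase 2 visits, give the existing Cocaine Craving Scale immediately before the witnessed spray and again at a fixed, stated time after it.
- Reconcile its frequency between Study Procedures, Phase 2, item 5 (weekly) and the SAP's Phase 2 Measures (three times a week).
- Add to the SAP a feasibility analysis: the mean within-visit change with a 95% confidence interval, allowing for repeated visits per patient. Make the placebo arm the main estimate of the route effect, show the oxytocin arm separately, and add a descriptive split by route of cocaine use (intranasal or smoked).
- State the form of the direct query and how its answers will be summarised.
- State the limits: with no no-spray comparator, the change also carries time and visit effects, and craving is a proxy for use.

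The protocol lists the scale at 2 minutes, so the added time is 18 × 2 = 36 minutes per patient at three visits a week, or 6 × 2 = 12 minutes if weekly, with no new instrument or procedure. The downside is that asking about craving before the dose may prime it slightly.

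The SAP already reports results for 26 randomised patients. If data collection is finished, the remaining action is to report that scores taken after the spray cannot answer the route question, and to correct the schedule for any continuation.
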